In addition to the incentive for completing assessments, we have budgeted up to \$50 for a clean (i.e., no evidence of tobacco and cannabis use) sample as a contingency management incentive at the final postpartum assessment (T4).

Participants will be paid using Vincent, the University's approved payment system. There will be no compensation for partial completion of T1, T2, or T3. At T4, participants will be paid separately for completing all questionnaires (\$75) and interviews (\$25).

5. Recruitment materials: (attach all material to be seen or heard by subjects, including advertisements and scripts)

	Document	Category	Date Modified	Document History
View	Recruitment Scripts(1)	Recruitment Materials	2/3/2026	History
View	Intervention Screening Survey(2)	Recruitment Materials	1/30/2026	History
View	Recruitment flyer(1)	Recruitment Materials	1/6/2026	History

Study Aims

1. * Describe the purpose, specific aims, or objectives and state the hypotheses to be tested:

Guided by the PICTURe community collaborative, we will conduct a single group, proof-of-concept feasibility trial of a new intervention designed to address prenatal depressive symptoms to encourage tobacco and cannabis cessation. We will examine the initial feasibility and acceptability of the intervention using standard measures in addition to measures suggested by the collaborative. We hypothesize that 1) the intervention will be feasible to participants and 2) the intervention will be acceptable to participants.

The primary outcomes of the trial are the feasibility and acceptability of the novel intervention and abstinence from tobacco and cannabis use. Feasibility and acceptability of the intervention will be assessed using attendance, completion of intervention-related procedures, and the Acceptability of Intervention Measure (AIM). Abstinence will be measured by proportion of the participants who self-report no use of either substance and by calculating the proportion of participants with negative urine screens for THC and COT. Secondary outcomes include changes in depressive symptoms, tobacco, and cannabis use from the baseline assessment in pregnancy to 3 months postpartum.

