A trained research team member will contact potential participants by telephone and/or email. We will use the relevant telephone and email scripts to describe the study and gauge interest. A screening survey will be used to determine eligibility. The screening survey will be programmed on REDCap and made available through Pitt+Me, the recruitment flyer, lab websites, and as a link sent to individuals who contact research staff directly. Once screened eligible, interested individuals will be contacted by the research assistant who will review and obtain consent for participation. After obtaining consent, the research team member will schedule the participant for their first prenatal session. The participant will then be texted or emailed a link to their baseline assessment questionnaires on REDCap.

Baseline Assessment (T1):

Participants will complete the following questionnaires as part of the baseline assessment: Demographics, EPDS, Smoking and Alcohol Use Questionnaire, Cannabis Use Questionnaire, Perceived Stress Scale-4, Major Experiences of Discrimination. Participants will be paid \$30 using the Pitt Vincent payment system when questionnaires are completed. The baseline assessment is estimated to take 30-60 minutes.

Prenatal Sessions

Participants will meet virtually with a study interventionist over the course of 6 prenatal sessions. Sessions will include education and discussions on the topics and strategies listed below. The scheduling timeline of prenatal sessions will depend on the gestational age of the pregnancy at time of enrollment and so will be determined on a case-by-case basis. Sessions will last up to 30 minutes.

1: Self-monitoring targets/ problem identification. This may include recognition of depressive symptoms, urges for tobacco and cannabis, how one might be used to manage withdrawal from the other.

2: Psychoeducation. This may include the teaching of rationale for addressing psychological distress/mood, relationship of trauma to mood and behaviors, model of cessation and relapse prevention/ learn how cannabis may hinder tobacco cessation and increase depressive symptoms.

3: Behavioral Activation. This may include identifying reinforcing activities and activities incompatible with tobacco and cannabis use.

4: Cognitive restructuring. This may include understanding/addressing dysfunctional thoughts about mood/stress and dysfunctional thoughts about tobacco and cannabis use.

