5: Mindfulness skills. This may include teaching of nonjudgmental emotional awareness, nonjudgmental awareness of management of urges, and trauma-informed adaptations to mindfulness practice.

End of Intervention Assessment (T2):

This assessment will occur when participants are 32-36 weeks gestation. Participants will complete the following questionnaires on REDCap as part of the end-of-intervention assessment: Demographics, EPDS, Smoking and Alcohol Use Questionnaire, Cannabis Use Questionnaire, Perceived Stress Scale-4, and Everyday Discrimination Scale. Participants will be paid \$50 using the Pitt Vincent payment system when questionnaires are completed.

1-month Postpartum Assessment (T3):

Participants will complete the following questionnaires on REDCap as part of the 1-month postpartum assessment: Demographics, EPDS, Smoking and Alcohol Use Questionnaire, Cannabis Use Questionnaire, Perceived Stress Scale -4, and Everyday Discrimination Scale. Participants will be paid \$70 using the Pitt Vincent payment system when questionnaires are completed.

3-month Postpartum Assessment (T4):

This assessment will be scheduled to occur in person at Bellefield Towers or at an agreed upon location convenient to the participant. Participants will complete the following questionnaires and interviews: Demographics, EPDS, Smoking and Alcohol Use Questionnaire, Cannabis Use Questionnaire, Perceived Stress Scale-4, Everyday Discrimination Scale, Acceptability of Intervention (AIM), Additional Treatments, Timeline Follow-back and OB/Neonatal outcomes. Following completion of the questionnaires and interviews, participants will be paid \$100 using the Pitt Vincent payment system. Participants will be asked to provide a urine sample as contingency management, which will be tested for the presence of cotinine (COT) and THC. Participants will receive an additional \$50 if their sample tests negative for both substances.

Urine collection:

Participant will be provided with a sterile urine collection cup and directed to a nearby bathroom where they can collect their sample independently. Participants will be offered an opaque bag to transport urine sample cup back to the assessment location. Research staff will follow testing procedures for the THC and COT dip tests and then dispose of all testing and collection equipment in a hazardous waste bin or bag.

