*** Provide a justification and describe the qualifications of the individuals who will obtain consent:**

[name], MS, has extensive training and experience in cognitive behavioral interventions with pregnant and postpartum people. She has provided evidence-based behavioral medicine interventions for smoking cessation, postpartum relapse, and worked on obesity, eating disorders, and smoking cessation trials. She also has

served as a trainer, providing training with manual-based research interventions for trainees and other interventionists. [name] will serve as primary interventionist and maintain responsibility for ensuring intervention materials and practices retain integrity over the course of the trial.

[name], MEd, is a Research Project Coordinator who has worked for the PI as part of the YoungMoms study for years and more recently as the coordinator for the PICTURE Study Collaborative. She has over a decade of experience working with pregnant and parenting people providing coaching, training, and behavioral intervention. [name] has recruited, consented, and conducted assessments for the YoungMoms study, including TimeLineFollowBack (TLFB) interviews and infant assessments. She is also familiar with IRB protocols and modifications.

Consent Forms

1. Consent Forms:

	Document	Category	Date Modified	Document History
View	PICTURE Intervention Consent Form(2)	Consent Form	2/3/2026	History

Refer to the following templates and instructional documents:

- Guidance - [Consent Wording](#)
- Template - Consent Document - [Short Form](#)
- HRP-090 - SOP - Informed Consent Process for Research
- HRP-091 - SOP - Written Documentation of Consent

Electronic Data Management

1. * Will only anonymous data be collected (select **NO** if identifiers will be recorded at anytime during the conduct of the study)?

☐ Yes ☒ No

Select all identifiers to be collected during any phase of the research including screening:

Name:		Internet Protocol (IP) Address:	
E-mail address:		Web Universal Resource Locators (URLs):	
Social security #:		Social security # (for Vincent payment only):	
Phone/Fax #:		Full face photo images or comparable images:	

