Emotional distress: Assessments and sessions will be conducted by highly trained interventionist with experience discussing depressive symptoms and prenatal substance use. Participation in the study is voluntary; prior to the visits, participants will be reminded that they can stop participating at any point. Similarly, participants may skip elements of the intervention or stop the session at any point. If a participant finds an element of the assessment or intervention upsetting, they can discuss it with the interventionist and will be given the opportunity to discuss it [name], a licensed clinical psychologist.

3. Financial risks - will the subject or insurer be charged for any research required procedures?

☐ Yes ☒ No

4. Describe the steps that will be taken to protect subjects' privacy:

Intervention sessions will be conducted in a private room or on a HIPAA-compliant version of Zoom. Before beginning the intervention session, the interventionist will remind the participant that sensitive topics related to substance use and mental health may be discussed and that they may prefer to be in a private location while discussing these topics. If someone other than the study participant is present, the interventionist will ask the participant if they are comfortable continuing with others present before beginning the session.

Participants providing a urine sample will obtain the sample independently in a private restroom stall. The participant will be offered an opaque bag in which to place the urine sample cup to further protect their privacy as they return to the location of the intervention session.

5. What steps will be taken in the event that a clinically significant, unexpected disease or condition is identified during the conduct of the study:

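### As written, the interventionist may run the in-person T4 visit, which collects the AIM and the final self-report of use; no independent assessor is assigned

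*Protocol*

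**What the plan says.** **Outcomes.** Study Aims, item 1 (repeated in substance in Study Design, item 3): "The primary outcomes of the trial are the feasibility and acceptability of the novel intervention and abstinence from tobacco and cannabis use". Acceptability includes the AIM. For abstinence, "Abstinence will be measured by proportion of the participants who self-report no use of either substance"; the second measure is obtained "by calculating the proportion of participants with negative urine screens for THC and COT".

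**Who assesses.** Risk and Benefits, item 2, under emotional distress: "Assessments and sessions will be conducted by highly trained interventionist with experience discussing depressive symptoms and prenatal substance use".

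**How each visit is done.** Research Activities, item 1, describes T1 as remote: "The participant will then be texted or emailed a link to their baseline assessment questionnaires on REDCap". The T2 and T3 questionnaires are also completed on REDCap. For T4 the description changes: "This assessment will be scheduled to occur in person at Bellefield Towers or at an agreed upon location convenient to the participant". The T4 paragraph lists questionnaires and interviews together and does not mention REDCap.

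**Staff.** Consent Process, item 5, describes two people. One "will serve as primary interventionist and maintain responsibility for ensuring intervention materials and practices retain integrity over the course of the trial". The other, a coordinator, "has recruited, consented, and conducted assessments for the YoungMoms study, including TimeLineFollowBack (TLFB) interviews and infant assessments". Neither is assigned to T4.

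**The concern.** The AIM asks participants how acceptable they found the intervention, and the use measures ask about tobacco and cannabis after several counselling sessions aimed at both. Answering to the person who gave that counselling invites socially desirable replies. The expected direction is the same for both: higher acceptability and more reported abstinence.

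Study Design, item 2, specifies a single arm. A two-arm trial with the same assessor arrangement might share some of this bias between arms; here there is no second arm to reveal or cancel it. The urine result gives a partial check on self-reported use at T4. Nothing comparable checks the AIM, and analysis cannot remove the bias once the data are collected.

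**Working it through.** The plan gives no figure to reproduce. The check is a comparison of sections, followed by one line of arithmetic for scale.

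**1. Mode and assessor by visit (Research Activities, item 1)**

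| Visit | Mode | Relevant data | Assessor named there |
|---|---|---|---|
| T1 | REDCap link sent to participant | Use questionnaires | None; participant completes |
| T2 | REDCap | Use questionnaires | None; participant completes |
| T3 | REDCap | Use questionnaires | None; participant completes |
| T4 | In person; REDCap not mentioned | Use questionnaires, Timeline Follow-back, AIM, urine test | Research staff for the urine test; nobody for the rest |

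The AIM and the Timeline Follow-back appear in the T4 row only.

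**2. Which self-reports are exposed.** Study Design, item 8, evaluates self-reported abstinence at Times 3 and 4. It calls Time 3 the end of pregnancy, while Research Activities places T3 at one month postpartum. The mismatch does not matter here, because T2 and T3 are both on REDCap. So one of the two abstinence time points involves no described assessor. Time 4 is the exposed one.

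**3. Who would run T4.** The T4 paragraph is silent on the questionnaires and interviews, so the reader falls back on Risk and Benefits, item 2, which names the interventionist. Other text is mixed:
- Item 2 also sends a participant upset by the assessment to the interventionist.
- Item 4 has the participant carry the urine cup back to where the intervention session takes place, although Research Activities calls it the assessment location and holds the sessions virtually.
- Item 5 speaks of an interviewer and of research assistants.
- Specimens and Related Data, item 3, leaves urine testing to research staff.

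No section places T4 with someone who did not deliver that participant's sessions.

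**4. What does not depend on the assessor.** Study Aims, item 1, bases its only stated feasibility and acceptability threshold on attendance (more than 70% of sessions), and acceptability also uses completion of self-monitoring forms. Urine cotinine and THC are measured, once, at T4.

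**5. Scale.** Study Design, item 1, gives 25 participants.
- One altered self-report: 1/25 = 0.04, or 4 percentage points.
- If one to three participants answered differently because of who was asking (an assumption): 1/25 to 3/25, or 4 to 12 points.

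The documents give no misreporting rate, so this range illustrates the sensitivity of a small denominator and is not an estimate. If the denominator is T4 completers, each answer weighs more.

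**The case against.** The strongest reply is that the sentence in Risk and Benefits is loose wording. It answers an ethics-form question about emotional distress and describes staff experience. Taken literally it also fails for T1 to T3, where nobody conducts anything. It does not say that the same interventionist treats and assesses a given participant, and calling one person the primary interventionist suggests there may be others.

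The protocol also separates questionnaires from interviews. At T4 they are paid separately, $75 and $25 (Recruitment Methods, item 4). The materials list in Research Activities, item 2, labels only the Timeline Follow-back and the self-reported medical record form as interviews. The AIM and the use questionnaires may therefore be self-completed at T4, and no section says that primary abstinence is taken from the Timeline Follow-back.

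Much of this stands, and it rules out stronger readings that a reader might infer:
- **That all self-reported abstinence and the AIM are given to the interventionist.** T1 to T3 are entered on REDCap, and the T4 mode for the AIM and use questionnaires is unstated.
- **That the primary conclusions rest wholly on these measures.** Attendance and urine results also contribute and are not open to this bias.
- **That a 4 to 12 point shift would consume most of the 15-point difference in Study Design, item 8.** That figure (25% − 10% = 15 points) comes from a comparison of INT with EUC. This single-arm trial has no EUC group, so the figure is not a valid comparator.

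What the reply does not supply is an assignment of T4 to anyone else. If an independent assessor is intended, the sentence in Risk and Benefits is wrong. If not, the arrangement is weak. The text needs correcting in either case. Urine testing does not settle it: self-report is a primary measure in its own right in Study Aims, and Study Design, item 8, places biochemical verification in a secondary analysis.

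**Conclusion.** The concern holds for T4. The only explicit statement about who conducts assessments names the interventionist, and nothing assigns the in-person visit to someone independent of delivery. Two components of the primary outcomes, the AIM and the T4 self-report of use, could therefore be collected by the counsellor whose work is being judged.

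The bias would probably be favourable, and the design offers no means of detecting or offsetting it, apart from the single urine check on use. Its size is unknown: 4 percentage points of self-reported abstinence per altered answer out of 25, with the number of altered answers unspecified.

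This rests on reading Risk and Benefits, item 2, literally and on social desirability acting in the usual direction. The documents do not establish that the sponsor has chosen to have counsellors assess their own participants. The point merits a correction before the first T4 visit; it does not undermine the trial as a whole.

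**What to change.** Amend the T4 paragraph of Research Activities, item 1, and the emotional-distress text in Risk and Benefits, item 2, to state that:

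- the T4 AIM and use questionnaires are self-completed on REDCap, as at T1 to T3, without the interventionist present;
- the T4 interviews and urine test are carried out by an existing team member (the coordinator or a research assistant) who did not deliver that participant's sessions.

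Then use one set of role words throughout: interventionist, interviewer, research assistant and research staff should each have a clear meaning in Research Activities, item 1, and Risk and Benefits, items 2, 4 and 5.

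The cost is a few sentences and a staffing roster. No new instrument or visit is needed. The coordinator already has assessment and Timeline Follow-back experience, so no new staff should be needed either. The drawback is slightly less scheduling flexibility at T4.
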